STUDY PROTOCOL

Effect of probiotics on T2DM and pre-diabetes in China ---the role of gut microbiota composition

Background

According to recent surveyed, diabetes prevalence rate in Chinese adults had gone up to 11.6%, the pre-diabetics diabetes prevalence rate was 50.1%. Effective intervention is urgently needed. Study of relationship between intestinal flora and diabetes is a hot topic at present. Gut microbiota disorders may be involved in the development of diabetes by means of increasing the number of inflammatory mediators, chronic inflammation, insulin resistance, increased energy intake, and obesity ect. In view of the correlation between gut microbiota and diabetes, gut microbiota can be taken as an important target for diabetes intervention. In this study, we aim to explore whether probiotics intervention affect blood glucose level and Risk factors for diabetes in T2DM and pre-diabetes via modification of gut microbiota composition and other post-interventional effects.

Objectives :

1. To investigate the effects of probiotics intervention on blood glucose metabolism (blood glucose, insulin sensitivity) and diabetes risk factors (blood lipid, weight, body composition, inflammatory state) in diabetes and pre-diabetes.
2. To investigate the effect of probiotics intervention on gut microbiota composition and its correlated metabolite.
3. To investigate the mediating effect of gut microbiota on glucose control in diabetes and pre-diabetes.

Methods/design

Trial design

This is a four-arm randomized controlled trial (Diabetes-intervention n=30, Diabetes-control n=30, prediabetes-intervention n=80, prediabetes-control n=80) . Participants are recruited from the outpatient registration pool of those who have participated in annual health checks for diabetes during 2017 to 2018 at Health care Center, Southwest Hospital, Chongqing, China. After an initial screening, potential subjects will be assessed for inclusion in the run-in trial. Those subjects who meet the inclusion criteria will be then invited to the intervention study for a total duration of 3 month. Those participants who are qualified for the intervention study will be randomized into intervention or control group after baseline assessments.

Eligibility criteria

Inclusion criteria:

1. The patient was diagnosed with pre-diabetes or diabetes by OGTT
2. Age: 18-60y
3. BMI:18-35kg/m²

Exclusion criteria:

1. Patients who have diabetes, hyperlipemia , and need regular use of drugs.

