after the intake of 75 g glucose for the assessment of serum insulin, and glucose. Venous blood samples will be taken in standardized fasting conditions at 7–8 a.m. Total cholesterol, high-density lipoprotein (HDL), low-density lipoprotein (LDL), triglycerides, will be measured from serum sample by conventional methods. ELISA can be used to assess serum samples for adiponectin, tumor necrosis factor alpha (TNF α), C-reactive protein (CRP), interleukin (IL-6), interleukin 10 (IL-10), and lipopolysaccharides (LPS). Gut microbiota metabolites will be measured from serum sample by LC-MS/MS.

3. Fecal samples collection

The fecal samples (two samples per each time) will be collected in the health care center during the second day of the 3-day dietary records collection. The study will provide to subjects the materials for sample collection. The subjects are advised to sample approximately 2–3 grams of feces by spatula attached to the cover of the plastic specimen jar. Fecal samples are frozen after collection within 30 min, stored at -80°C . 16SrDNA sequencing will be performed. Different bacterial indices will be calculated to evaluate the interrelationship of different bacterial species and how they are associated with diabetes.

4. Body composition

Bioelectrical impedance analysis will be used to estimate lean tissue mass (LM), fat mass (FM) and bone mass (BM) of the whole body, legs, arms, and trunk as well as android and gynoid regions.

Concomitant adherences and procedures

To ensure good compliance in probiotics and placebo group, we will keep in contact with them via phone call monthly questionnaire to check on their physical condition and lifestyle at 1 and 3months follow-up during the intervention.

Sample size estimation

The sample size calculation with an estimate of how many participants will be needed for the primary outcome to be statistically, clinically and/or politically significant. For the specific primary outcome of blood glucose and microbiota, based on our pilot study, 68 prediabetes subjects in each group would have 85% power for mean comparison between the randomized groups for the fast

blood glucose. We set the significance level at 0.05 and allowed for 10 mean comparisons with the Bonferroni correction between the groups. Taking into account the compliance and drop-out (15%), we increase our sample size to 80 in each prediabetes group. With the same approach, sample size for each diabetes group is 60 subjects.

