Randomization methods

1. Randomization Process:

SPSS will be used for generating the randomization assignment for Diabetes groups and prediabetes groups respectively. Randomization numbers will be generated and sealed in an envelope and kept by the study coordinator. On the basis of subjects' enrolment time when 20 qualified subjects are reached, the study coordinator will open one block to allocate subjects into each group.

2. Blinding:

Both subjects and investigators will be blinded with respect to the randomization assignment of each participant. The investigators will remain blinded until the completion of the study. The study coordinator will be blinded from which group the participants are signed in. The accuracy of the randomization log is the responsibility of the study coordinator.

Statistical methods

All data collected by questionnaires will be entered into database management software (EpiData), double checked by independent researchers, and exported to SPSS statistics version. If data is not normally distributed, their natural logarithms will be used for further analysis.

Descriptive statistics will be used to present the background and anthropometric data at the baseline and follow-up assessments as mean and 95% confidence interval (CI) unless otherwise stated.

An intention-to-treat (ITT) analysis will be performed to compare the Probiotics group to Placebo group. The effects of the interventions will be assessed using analysis of variance (ANCOVA) for repeated measures (treatment group \times time) and baseline difference as a covariate. If the significance of the group by time interaction is $p < 0.05$, the effect will be localized utilizing Bonferroni for multiple comparisons. The level of statistical significance chosen for the contrasts will be $p < 0.05$. In addition to the ITT

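### The planned diabetes group size is 30 per group in the trial design but 60 per group in the sample-size section, and neither document reconciles them

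*Protocol*

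**What the plan says.** The protocol gives the diabetes group size twice.

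- **Methods/design, Trial design** lists the four arms as "Diabetes-intervention n=30, Diabetes-control n=30, prediabetes-intervention n=80, prediabetes-control n=80".
- **Sample size estimation** starts with prediabetes: "68 prediabetes subjects in each group would have 85% power for mean comparison between the randomized groups" on fasting glucose. On multiplicity it says "We set the significance level at 0.05 and allowed for 10 mean comparisons with the Bonferroni correction between the groups". It then inflates for losses: "Taking into account the compliance and drop-out (15%), we increase our sample size to 80 in each prediabetes group". The last sentence of the section turns to diabetes: "With the same approach, sample size for each diabetes group is 60 subjects".

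The two populations are randomised separately, and under Randomization Process the allocation is released in blocks: "when 20 qualified subjects are reached, the study coordinator will open one block to allocate subjects into each group". No total sample size is stated in the protocol. The SAP repeats the protocol's statistical methods and contains no sample size.

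**The concern.** Diabetes is one of the two populations in the title and objectives. It has its own randomisation and its own sample-size statement. A factor of two in its planned size is therefore a contradiction in a basic design fact.

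The wording makes the ordinary reading 60 per group. The preceding sentence gives 80 for each prediabetes group, a per-group number that matches the trial design. The diabetes sentence is built in parallel and claims the same approach, meaning 85% power, the same Bonferroni allowance and the same 15% loss. If that is what was calculated, the trial design plans half the required number.

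At stake is whether the diabetes comparison was planned at its calculated size. A reader who later sees a null diabetes result could not tell whether the planned size was meant to detect the effect of interest.

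**Working it through.** **Inputs.** From Trial design: 30 per diabetes group and 80 per prediabetes group. From Sample size estimation: 68 evaluable per prediabetes group, 85% power, alpha 0.05 with Bonferroni for 10 comparisons (0.05/10 = 0.005 each), 15% loss, 80 randomised per prediabetes group, 60 per diabetes group. Not given: the difference or SD for either population, the evaluable number for diabetes, and whether tests are one- or two-sided.

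**Step 1: the plan's own inflation step.** Randomised n = evaluable n / (1 − loss). For prediabetes, 68 / 0.85 = 80. This reproduces the stated figure and agrees with the trial design. It confirms only the drop-out step; the 68 cannot be reproduced without the pilot difference and SD.

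**Step 2: does the inflation step favour 30 or 60 for diabetes?** 51 / 0.85 = 60, and 25 / 0.85 = 29.4, which rounds up to 30. Both fit.

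**Step 3: does the block size favour one?** A total of 2 × 30 = 60 is 3 blocks of 20. A total of 2 × 60 = 120 is 6 blocks of 20. Both fit.

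**Step 4: totals.** 2 × 30 + 2 × 80 = 220. 2 × 60 + 2 × 80 = 280. No stated total exists to compare with either.

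Nothing in the documents therefore decides between two readings.

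- **Reading A:** 60 per group was required and 30 per group is planned.
- **Reading B:** 60 is the two groups together, and the per-group wording is wrong.

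**Step 5: consequence under Reading A.** Method: noncentral t for an unadjusted two-sample comparison, n evaluable per group, df = 2n − 2, noncentrality d√(n/2). First find the d that gives 85% power at 60 × 0.85 = 51 evaluable. Then compute power for that d at 30 × 0.85 = 25.5, taken as 25 and 26.

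| Alpha, sides | d for 85% power, n = 51 | Power, n = 25 | Power, n = 26 |
|---|---|---|---|
| 0.005, two-sided | 0.776 | 43.1% | 45.3% |
| 0.05, two-sided | 0.599 | 54.6% | 56.3% |
| 0.005, one-sided | 0.727 | 46.3% | 48.4% |
| 0.05, one-sided | 0.535 | 58.7% | 60.1% |

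**Step 6: consequence under Reading B.** There is no shortfall against plan. The difference detectable with 85% power, two-sided and unadjusted, is:

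| Alpha | n = 25 | n = 26 |
|---|---|---|
| 0.005 | 1.134 SD | 1.110 SD |
| 0.05 | 0.865 SD | 0.847 SD |

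For comparison, 68 evaluable per prediabetes group corresponds to about 0.67 SD at two-sided alpha 0.005.

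**Step 7: baseline adjustment.** The planned analysis is a baseline-adjusted repeated-measures ANCOVA. As a rough guide, multiply the detectable difference by √(1 − r²), where r is the baseline correlation; r is an assumption, because the documents give none. With r = 0.5 the Reading B values become 0.96–0.98 SD (alpha 0.005) and 0.73–0.75 SD (alpha 0.05). With r = 0.7 they become 0.79–0.81 and 0.60–0.62 SD. The Reading A percentages hardly change, because adjustment rescales the effect equally at both sizes.

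**The case against.** The strongest reply is that 30 + 30 is exactly 60, so one wrong word explains everything. On that reading the trial is not short of its plan and the repair is a phrase. This may well be the likelier explanation. The documents do not say so, however, and the parallel prediabetes figure is plainly per group. The objection bears on which sentence to change. It does not remove the contradiction, because the sample-size sentence is wrong as written even if the objection is right.

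A second reply is that the magnitudes are hypothetical. That is fair. The documents contain no diabetes effect size. The Reading A percentages are back-calculated from an assumed 85% power, and the Reading B values would apply to any comparison with 25 or 26 per group. The adjustment factor in Step 7 belongs to a single-follow-up ANCOVA, not to the planned group-by-time test over two follow-up visits, so those values are only indicative.

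Third, the missing difference and SD affect prediabetes as well, and choosing 30 or 60 would not supply them. This also stands: it is a related reporting gap, and the contradiction does not depend on it.

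Finally, a null result is read mainly from its confidence interval, which the contradiction leaves untouched. That is correct. What is lost is the ability to judge the result against what the trial was planned to detect.

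**Conclusion.** The concern holds. The protocol states two incompatible sizes for two of its four arms, differing by a factor of two, with a planned total of 220 or 280. Confidence in this is high, because it needs only the two sentences and no assumption. It must be fixed, since only the sponsor can say which figure was intended.

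The power loss is conditional. It applies only under Reading A and assumes an unadjusted t-test, 15% loss and 60 per group as the size giving 85% power. Power would then be 43–45% at two-sided alpha 0.005 or 55–56% at 0.05; one-sided, 46–48% and 59–60%. Under Reading B the power was never reduced and only the wording is wrong.

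**What to change.** Make Trial design and Sample size estimation agree on the diabetes group size.

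- **If 30 per group stands:** correct the last sentence of Sample size estimation to 30 in each diabetes group, 60 in total, and restate the power or detectable difference that this gives after 15% loss. The cost is one corrected sentence and one restated sentence.
- **If 60 per group was calculated and planned:** correct the counts in Trial design. The stated planned total becomes 280 instead of 220. That is the sponsor's decision and is not requested here.

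In both cases, state for diabetes the pilot difference, the SD, the alpha used (0.005 or 0.05), one- or two-sided testing, the evaluable number per group and the resulting power under the planned analysis. The SD values in this note are illustrations and should not be copied into the protocol. No additional enrolment is asked for.

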2. Secondary obesity or diabetes.
3. Serious systematic diseases, such as digestive diseases, tumor, cardiac, pulmonary, renal, rheumatic and immune system diseases.
4. Pregnant women, women ready for pregnancy, and nursing mothers.
5. Take antibiotics or bacterial agents within 1 month
6. Diarrhea or abscess in 1 month or blood or other abnormal feces
7. Diabetics history more than 2 years
8. The OGTT experiment $FG \geq 9 \text{ mmol/L}$ or $2h \geq 14 \text{ mmol/L}$ in diabetic patients

Study settings

The interventions and laboratory tests and performed and managed at the Health Care Center, Southwest Hospital, Chongqing, and Health management institute, PLA General hospital, Beijing, China.

Trial design

Interventions

1. Probiotics group: Diabetes/prediabetes participants take four packs of probiotics a day on an empty stomach with 200ml water every morning. The probiotics is called KAWAI, each pack contains 880 billion dead *Lactobacillales* (*S. thermophilus*) .
2. Placebo group:
Diabetes/prediabetes participants take four packs of probiotics a day on an empty stomach with 200ml water every morning.

Primary and secondary outcomes

Primary outcomes:

1. Blood glucose levels(FBG and OGTT), insulin sensitivity(Insulin, C-peptide)
2. Gut microbiota composition

Secondary outcomes:

1. Blood inflammatory markers
2. Diabetes risk factors (blood pressure, blood lipids)
3. Weight, waist circumference, BMI, Body composition
4. Intestinal endocrine function (GPL-1)
5. Gut microbiota metabolites

The primary and secondary outcome measures will be assessed at baseline, 1- and 3-month time points.

Measurements procedures

1. Screening:

The potential subjects will be selected from the outpatient pool of those who have records of abnormal blood glucose level in 2017. Registered nurses from health care center will first contact the potential subjects and invite them to a

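### The analysis is called ITT, but the named repeated-measures ANCOVA has no rule for missed visits and by default keeps only participants with complete follow-up

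*Protocol*

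**What the plan says.** Protocol, Statistical methods, and SAP, Statistical plans, use the same wording on this point.

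- Population: "An intention-to-treat (ITT) analysis will be performed to compare the Probiotics group to Placebo group". Neither document says who belongs to the ITT set when a visit is missed.
- Method: "The effects of the interventions will be assessed using analysis of variance (ANCOVA) for repeated measures", with a treatment group by time term and "baseline difference as a covariate". A later sentence, on percentage changes, adjusts for the baseline value instead.
- Software: data are "exported to SPSS statistics version". No SPSS procedure is named.
- Visits (Protocol, Primary and secondary outcomes): "The primary and secondary outcome measures will be assessed at baseline, 1- and 3-month time points".
- Expected loss (Protocol, Sample size estimation): "Taking into account the compliance and drop-out (15%), we increase our sample size to 80 in each prediabetes group".
- A second analysis, additional to the ITT analysis, applies at compliance of 60% or more.

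Neither document mentions imputation, a mixed model, or a sensitivity analysis for missing data.

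**The concern.** An ITT analysis should use everyone randomised, as allocated. Classical repeated-measures ANCOVA needs a complete row per person, so by default it removes anyone who misses month 1 or month 3. A participant measured at month 1 who then leaves contributes nothing, even to the month-1 comparison. The label and the default behaviour of the named method pull apart, and no text settles which prevails. The rule could therefore be chosen after the data are seen.

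What is at stake is bias. If those who leave after month 1 are selected on their month-1 glucose, and the selection differs between probiotic and placebo, the completers are no longer comparable by randomisation. The discarded month-1 values are the data that could correct for this.

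**Working it through.** **1. The plan's own figure.** Inputs from Protocol, Sample size estimation: 68 per prediabetes group at 85% power, 15% allowance.

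68 / (1 - 0.15) = 80, which reproduces the stated size. The plan therefore provides for 0.15 x 80 = 12 per prediabetes arm, or 24 of 160, not contributing. The allowance covers compliance as well as drop-out, and a non-complier who attends visits stays in an ITT analysis. So 12 per arm is an upper planning figure.

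**2. Inputs for the bias check (all assumed).** The documents give no effect size, SD, visit correlations or dropout model.

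- True effect: -0.67 SD at both months. For scale, the plan's 68 per group at 85% power and Bonferroni alpha 0.05/10 = 0.005 (taken as two-sided) implies d = (2.807 + 1.036) x sqrt(2/68) = 0.659 SD.
- Dropout after month 1, with Y1 the month-1 glucose in SD units: logit P(drop) = a + b x Y1. The intercept a is set in each arm to give 15% loss; b is 0, +1 or -1.
- Correlations: equal at 0.5, equal at 0.7, or 0.6 (baseline to month 1), 0.5 (baseline to month 3) and 0.7 (month 1 to month 3).

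**3. Estimators.**

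- Completers only: regress the month-3 value (or month-1 value) on arm and baseline, among those with both visits.
- Likelihood, for this dropout pattern: regress Y1 on arm and baseline in everyone (arm coefficient B1). Regress the month-3 value on arm, baseline and Y1 in completers (arm coefficient G1, Y1 coefficient G2). The month-3 effect is G1 + G2 x B1.

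**4. Results** (simulation, 1,000,000 per arm, so the figures show bias rather than sampling noise). Here placebo loses its high-glucose participants; in the opposite case the probiotic arm also loses its low-glucose participants.

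| Correlations | Dependence on Y1 | Completers, month 3 | Month-3 bias | Month-1 bias | Likelihood, month 3 |
|---|---|---|---|---|---|
| all 0.5 | placebo only | -0.64 | 0.03 | 0.10 | -0.67 |
| all 0.5 | opposite | -0.60 | 0.07 | 0.20 | -0.67 |
| all 0.7 | placebo only | -0.64 | 0.03 | 0.07 | -0.67 |
| all 0.7 | opposite | -0.61 | 0.06 | 0.14 | -0.67 |
| 0.6, 0.5, 0.7 | placebo only | -0.62 | 0.05 | 0.09 | -0.67 |
| 0.6, 0.5, 0.7 | opposite | -0.56 | 0.11 | 0.18 | -0.67 |

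- Swapping the arms reverses the sign, so the bias can flatter or penalise the product.
- With no true effect, the same patterns give false differences of about the same size.
- With random dropout, or equal slopes and 15% lost in each arm, completers give -0.67: no bias.
- The likelihood month-1 estimate is also -0.67 throughout.

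**5. Scale.** As a share of the assumed effect, one-arm bias at month 3 is 0.03/0.67 = 4% to 0.05/0.67 = 7%. Opposite dependence gives 0.06/0.67 = 9% to 0.11/0.67 = 16%. The standard error of a baseline-adjusted contrast with 68 per arm is sqrt(2 x (1 - r^2)/68), which is 0.149 SD at r = 0.5 and 0.122 SD at r = 0.7. Every month-3 bias above is below one standard error.

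**The case against.** The documents do not say that only participants with every visit are analysed. A reader might infer that from the method's name, but no SPSS procedure is named and neither imputation nor a mixed model is excluded. Because ITT is set against the analysis at 60% compliance or more, it may mean no more than analysis regardless of compliance. This stands: deletion of incomplete participants is a default of the named method, not a stated rule.

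A reader might also infer that about 15% of participants will be excluded. The text does not support that, since the figure combines compliance with drop-out and is a sizing allowance for the prediabetes groups.

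The route to bias is conditional. The protocol mentions feedback in Follow-up visits and in Methods of measurements, but never says that glucose results are disclosed. Participants and investigators are blinded, which makes the same dependence in both arms more natural than different dependence. A single dropout rule shared by both arms, with 15% lost overall, gives no bias when there is no effect. With a true -0.67 SD and slope 1, it gives about -0.65 to -0.66. This also stands, and it limits the point to a modest one.

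Finally, "baseline difference as a covariate" might be read as an unusable covariate, because a between-group difference is constant within an arm. The later adjustment for the baseline value shows the likely intent, so this is a wording correction and adds no weight to the ITT point.

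None of this supplies the missing rule. The plan still does not say what happens to a participant with one follow-up visit.

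**Conclusion.** The point holds as a cheap improvement that should be made. The plan promises ITT, names a method that in its classical form defaults to complete cases, and gives no rule for missed visits. Up to 12 of 80 per prediabetes arm could be lost under the plan's own allowance.

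If dropout depends on month-1 glucose differently by arm, the completers-only month-3 estimate is off by about 0.03 to 0.05 SD (one arm) or 0.06 to 0.11 SD (opposite directions). At month 1 it is off by about 0.07 to 0.20 SD. If dropout is random or equally dependent in both arms, the bias is about zero. These sizes rest on the assumed effect, loss, slope and correlations. They show what could happen, and are not a forecast that the trial's result will be biased.

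**What to change.** In Protocol, Statistical methods, and SAP, Statistical plans:

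- Define the ITT set as all randomised participants, analysed as allocated.
- Replace repeated-measures ANCOVA with a likelihood-based mixed model for repeated measures (SPSS MIXED) on all available month-1 and month-3 values. Include treatment by visit and the participant's own baseline value by visit, and report the month-1 and month-3 contrasts.
- Participants with no follow-up value add no outcome data to this model. Report their number by arm, and add a sensitivity analysis for data not missing at random.
- Use one phrase for the covariate throughout: the participant's baseline value of the outcome.

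The cost is new wording, a different procedure in the same software and slightly more analysis work. No new data are needed. The model relies on data being missing at random given baseline, arm and month-1 value. That is a weaker assumption than the completers-only analysis needs, but it cannot be verified from the data, hence the sensitivity analysis.

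### Where the analysis plan names a multiplicity adjustment it uses Bonferroni; Holm step-down would control the same familywise error and never reject less, for a small, conditional gain in power.

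*Protocol*

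**What the plan says.** Bonferroni is the only multiplicity method the documents name. It appears in three roles.

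- **Sample size** (Protocol, Sample size estimation): "We set the significance level at 0.05 and allowed for 10 mean comparisons with the Bonferroni correction between the groups". The resulting claim is that "68 prediabetes subjects in each group would have 85% power for mean comparison between the randomized groups for the fast" blood glucose outcome.
- **Follow-up of an interaction** (Protocol, Statistical methods; SAP, Statistical plans): if the group by time interaction has p < 0.05, "the effect will be localized utilizing Bonferroni for multiple comparisons".
- **Percentage change from 0 to 3 months** (same sections): the ANCOVA with compliance and treatment group as factors also uses Bonferroni.

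Other inferences in those sections name no adjustment: the contrast to control after a significant overall group difference, the rule that a 95% CI excluding zero counts as significant, and the correlation and regression analyses. The ten comparisons are not listed, and the analysis text does not say which tests form a family.

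**The concern.** Single-step Bonferroni holds every test in a family of m at alpha/m, even after some have been rejected. Holm orders the p-values and tests them at alpha/m, alpha/(m-1), and so on up to alpha, stopping at the first failure. It controls familywise error under any correlation, as Bonferroni does, and cannot reject less. For accept/reject decisions it is therefore at least as good.

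The trial measures fasting and OGTT glucose, insulin and C-peptide at 1 and 3 months. A working product could plausibly move several of these. That is the setting in which Holm helps, so some chance of confirming second and later effects may be given up for no gain in error control.

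**Working it through.** **Inputs from the documents.** Alpha 0.05, 10 comparisons, 85% power, 68 evaluable per prediabetes group, 15% drop-out (Sample size estimation); follow-up at 1 and 3 months (Primary and secondary outcomes).

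**Assumptions.** Two-sided tests; normal test statistics; no adjustment for baseline; correlations and effect sizes as stated below. The Protocol gives no difference or SD and says only that the calculation is "based on our pilot study".

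**Step 1: the plan's own figures.** Drop-out: 68 / (1 - 0.15) = 80, as stated. The 68 cannot be reproduced without an effect size. Solving backwards at alpha 0.05/10 = 0.005:

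d = (z₀.₉₉₇₅ + z₀.₈₅) × √(2/68) = (2.807 + 1.036) × 0.1715 = 0.66 SD.

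This is what the 68 implies; it does not confirm it.

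**Step 2: two visit contrasts per outcome.** With two arms and visits at months 1 and 3, localization involves about two between-arm contrasts. The Bonferroni critical value is z₀.₉₈₇₅ = 2.241. Each statistic has mean d × √(68/2) = 5.831d. At d = 0.40, Bonferroni power is Φ(2.332 - 2.241) = Φ(0.091) = 54%. Holm adds the cases in which this contrast falls between 1.960 and 2.241 and the other exceeds 2.241. By simulation, with correlation 0.7, both effects real and the interaction gate ignored:

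| Effect (SD) | Bonferroni | Holm | Gain (points) |
|---|---|---|---|
| 0.40 (assumed) | 54% | 59% | about 5 |
| 0.45 (assumed) | 65% | 70% | about 5 |
| 0.50 (assumed) | 75% | 80% | about 5 |
| 0.66 (back-solved) | 94.5% | 96.3% | about 2 |

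At 0.40 SD the chance of detecting both visits rises from 41% to 51%. If only one visit has a real effect, the gain is under 0.2 points across these effect sizes.

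**Step 3: the interaction gate.** Localization happens only if the interaction has p < 0.05. The size of the gain depends on what time means in the model.

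- If baseline is only a covariate and time means months 1 and 3, equal effects at both visits produce no interaction, and the gate opens about 5% of the time. For 0.40 to 0.50 SD, power per contrast is then about 2.6-3.4% with Bonferroni and 2.8-3.7% with Holm, a gain of at most about 0.3 points.
- If baseline is a level of time, most of the gain remains: 49% to 54% at 0.40 SD.

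**Step 4: ten comparisons, if analysed as one family.** Each real effect has 85% power at 0.005; correlation 0 to 0.5.

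| Real effects of ten | Bonferroni, average power | Holm, average power |
|---|---|---|
| 1 | 85% | 85% |
| 3 | 85% | 86% |
| 5 | 85% | 88% |
| 8 | 85% | 90-92% |
| 10 | 85% | 93-96% |

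With five real effects, the chance of detecting all five rises from 44-60% to 55-68%. Holm's simulated familywise error was at most 0.048. The chance of at least one true finding changes by less than 0.2 points.

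The gain for the percentage-change ANCOVA is not worked out, because its family size is not stated.

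**The case against.** Bonferroni is a legitimate choice, and several stronger readings that a reader might infer do not survive the text.

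- *Every multiple comparison uses Bonferroni.* No: the contrast to control, the CI rule and the correlation and regression analyses name no adjustment.
- *Power is lost on every comparison after the first.* No: Holm relaxes the threshold only after a rejection. If the smallest p-value fails at alpha/m, the two methods agree.
- *The planned 85% for fasting glucose is eroded.* No: the sample size says that it already "allowed for 10 mean comparisons with the Bonferroni correction between the groups".
- *The outcomes are tested together at alpha/10.* The analysis text does not say so; the ten appear only in the sample size. The gains in Step 4 are therefore conditional and should not be the headline.

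Two further objections stand. The gate can remove most of the gain when effects are equal at both visits. And Bonferroni gives simple simultaneous intervals, whereas Holm has no equally simple match. That matters in a plan that also decides significance by intervals, although the intervals it specifies are ordinary 95% ones.

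The undefined family, and whether p < 0.05 for the contrasts is an adjusted value, are more important gaps. They are separate points: they limit how well the benefit can be quantified but do not reverse its direction.

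**Conclusion.** The point holds as an optional improvement in efficiency. That Holm never rejects less at the same familywise error is mathematical and needs no trial figure. The size of the benefit does depend on assumptions. For two visit contrasts with both effects real and the gate ignored, it is about 5 points per contrast at 0.40-0.50 SD and about 2 points at 0.66 SD. It is near zero with one real effect, and at most about 0.3 points if the gate opens only by chance. Gains of 8 to 11 points require ten comparisons in one family, all real, each at 85% power. These figures are for the prediabetes groups; the diabetes groups were not worked out because their size is given both as 30 and as 60 per group.

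**What to change.** In the Protocol (Statistical methods) and the SAP (Statistical plans), replace Bonferroni with Holm step-down (Holm-Bonferroni) in the two sentences that name it: localization after the interaction, and the percentage-change ANCOVA. State in each which comparisons form the family. Leave the sample size at alpha/10; taken as stated, its 85% then becomes a lower bound.

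Add that Holm-adjusted comparisons are decided by their adjusted p-values and not by whether a 95% CI excludes zero. Any simultaneous intervals stay at Bonferroni width, so an interval and its Holm decision may occasionally disagree; the SAP should say that the p-value governs.

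The cost is wording only, with no extra participants, visits or data, since Holm needs only the unadjusted p-values. Make the change before unblinding.
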